15.2 Sample Size Justification

We aim to recruit up to 80 subjects to achieve a final sample size of 60 evaluable subjects. For Aim 1, the **sample size of 60** (30 in initial sildenafil group and 30 in initial placebo group), gives 80% power for a relatively small effect size of 0.37 for the change in %BAD in the sildenafil versus placebo periods (using a paired t-test, although we will use a linear mixed model for the analysis). Based on previous studies in diabetes, with equivalent CV risk, the estimated standard deviation (SD) of %BAD is approximately 4. The effect size of 0.37 thus corresponds to a % increase of 1.5%, which is clinically meaningful. We will analyze drop-ins, drop-outs, withdrawals, and non-adherences according to intention-to-treat principles.

For Aim 2, given that we are using the same analysis strategy as Aim 1, the sample size of 60 (30 in each group) again yields 80% power to detect an effect size of 0.37 for the change in a given biomarker. The estimated power (in either aim) corresponding to the final mixed model is difficult to estimate more

specifically since it is unclear how much residual variability will remain after adjusting for other covariates, and/or whether a stronger association will be evident after model adjustment.

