5.2.1 Brachial Artery Flow Mediated Dilation (FMD) Without Nitroglycerin

The methods of assessment of endothelial function via FMD will be performed following guidelines. Vascular reactivity will be measured noninvasively using vascular ultrasound imaging. Flow and diameter changes of the brachial artery will be assessed by Duplex ultrasound using a high-resolution linear array transducer. The difference between the maximum brachial artery diameter (BAD) post-occlusion and the baseline diameter is expressed as a percentage (%BAD). Generally, %BAD values below 5-7% represent endothelial dysfunction, which is associated with CV risk factors, future CVD and mortality. Effective treatment of risk factors may improve endothelial function. Given its reversibility and non-invasiveness, brachial artery FMD is attractive as an assessment tool to monitor strategies to reduce CVD.

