9.2 Justification of study drug selection

This dose was chosen because it is the usual dose used and FDA-approved for the treatment of erectile dysfunction (ED), with a known favorable safety profile at that dose. Furthermore, this was the dose used in a double-blind, placebo-controlled, prospective trial of 24 men with type 2 diabetes with ED, wherein it was shown that daily use of sildenafil 50 mg/day for 10 weeks resulted in improved endothelial function as measured by brachial arterial FMD.

Sildenafil 50 mg orally once daily for 3 months will be provided in bottles during the sildenafil treatment periods.

Placebo pills with the same size, shape, color, and texture as sildenafil will also be provided in bottles, to be taken orally once daily for 3 months during the placebo periods.

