15.3 POTENTIAL PITFALLS AND SOLUTIONS

15.3.1 How will we account for the potential variability in results of brachial artery FMD measurements?

A number of factors may potentially influence the results of brachial artery FMD. To account for this, subject-specific factors will be minimized by requesting subjects to limit antioxidant vitamin and/or antioxidant-rich diet within 72 hours; document use of CV medications (e.g., β -blockers, calcium channel blockers, NSAIDs, and aspirin); limit tobacco and caffeine use within 12 hours; document the phase of menstrual cycle for premenopausal women (since optimum time for FMD studies is days 1-7 of menses); abstain from exercise within 12 hours; and be fasting and rested before the FMD study. Finally, since we recognize there is diurnal variation in the FMD response, we will attempt to schedule each subject's visits at consistent times of the day.

15.3.2 What if study subject recruitment and retention rates are slower and/or less than anticipated?

We will increase advertising efforts and may open the study at other community rheumatology clinics, with over 6,000 active RA patients. We may include those on statins, ACE-i or ARB (on stable dose x 4+ months), and retain subjects with RA medication changes. We will address these factors statistically, if needed.

15.3.3 How will the effect of comorbidities and RA disease-related factors that affect endothelial function be mitigated so as not to confound the results of sildenafil's effect on endothelial function?

A potential confounder is the effect of traditional CVD risk factors (e.g., DM), CV medications, RA medications, disease activity and duration on potential change in endothelial function over time. As described in Section 4.4, we plan to adjust for these through multivariable linear mixed models. Furthermore, subjects who require a new start or change in RA medication or glucocorticoid maintenance dose increase to 10 mg/day or greater for 4+ weeks during the trial will be withdrawn from the study. Since this is a randomized placebo-controlled study, we anticipate the frequency of these potential confounders will be similar between groups.

15.3.4 Will potential effects of sildenafil risk un-blinding due to altered erectile function or headaches?

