15.4 Interim Analyses

Potential non-compliance (assessed via pill counts) will be analyzed using intention-to-treat strategy, and for missing data, we will conduct a sensitivity analysis to conservatively assess observing how the worst outcome (of %BAD) would affect results. The test of a treatment \times period interaction is not possible in the given cross-over design since it is confounded by the group effect.

We do not anticipate many subjects with RA or CV medication changes, since inclusion criteria state no expected therapy changes over next 6 months. Moreover, such changes are unlikely to occur systematically more often in the initial sildenafil vs. placebo groups. However, in the event there are many with such changes, we will also conduct a secondary sensitivity analysis including them to assure this does not affect results. The %BAD was chosen as the primary outcome on which to calculate sample sizes based on clinical considerations. Specifically, %BAD has been validated longer and in more populations than PAT.

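### %BAD and PAT are both primary at two-sided 0.05 with no rule for declaring success; a minor point is that the SD behind the 1.5-point effect in section 15.2 is not identified

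*Combined protocol and SAP*

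**What the plan says.** **Primary outcomes.** The synopsis defines the primary variable through both FMD and PAT. Section 12.1 lists both as primary efficacy outcomes, and section 15.1 numbers them (1) and (2) with equal rank. Section 15.1 sets two-sided 0.05 for all tests. It gives no order, no split of alpha, and no statement that either or both must succeed. The nearest text is in section 15.4: "The %BAD was chosen as the primary outcome on which to calculate sample sizes based on clinical considerations". That sentence says which outcome drove the sample size. It does not say how success will be declared.

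**Sample size.** Section 15.2 claims 80% power with 60 evaluable subjects at a standardised effect of 0.37 for the change in %BAD between the sildenafil and placebo periods, calculated "using a paired t-test, although we will use a linear mixed model for the analysis". It then gives the variability: "Based on previous studies in diabetes, with equivalent CV risk, the estimated standard deviation (SD) of %BAD is approximately 4". From these it concludes: "The effect size of 0.37 thus corresponds to a % increase of 1.5%, which is clinically meaningful". No within-subject correlation is given, and no SD is named as that of the difference between periods.

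**The concern.** With two equally ranked primary outcomes and no rule, a trial that is significant on one and not on the other has no agreed reading. It could be reported as positive because a primary outcome was met, or as negative because the other was not, and the choice could be made after the results are known. If either result suffices, the false-positive risk for the primary claim is nearly double the stated 5%.

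The minor point concerns what the sample size means on the clinical scale. The 1.5-point figure is the only stated link between 60 subjects and a clinically meaningful effect. A paired t-test standardises by the SD of the within-subject difference, whereas section 5.2.1 defines %BAD from a single test (post-occlusion maximum against baseline diameter). Multiplying 0.37 by an SD of %BAD is valid only if that SD happens to equal the SD of the difference, and section 15.2 does not say that it does.

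**Working it through.** **Inputs from the documents:** 60 evaluable subjects, effect size 0.37, 80% power, paired t-test, SD about 4, 1.5 points (section 15.2); two-sided 0.05 and two primary outcomes (section 15.1). **Assumptions, because the documents give no value:** the correlation between the two test statistics, the effect size on PAT, and the within-subject correlation rho of %BAD.

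**1. The plan's own figure.** Paired t-test, df = 59, noncentrality = 0.37 × √60 = 2.866, critical value 2.001. Power from the noncentral t distribution is 80.5%. The effect size with exactly 80% power is 0.3677. A comparison of 30 versus 30 independent subjects at 0.37 would have only about 30% power, so 0.37 fits the paired reading. Also 0.37 × 4 = 1.48, rounded to 1.5. Section 15.2 reproduces.

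**2. Family-wise error if either outcome suffices.**
- Independent tests: 1 − 0.95² = 9.75%.
- Test correlation 0.5 (bivariate normal): about 9.1%.

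**3. Testing %BAD first, then PAT.** PAT can be claimed only after %BAD has been rejected at 0.05, so the family-wise error is at most 5%. %BAD is tested exactly as planned, and its power stays at 80.5%. PAT is claimed only if both tests are significant. If the PAT effect were also 0.37:
- tested alone: 80.5%
- in sequence, independent tests: 0.805² = about 65%
- in sequence, test correlation 0.5 (bivariate normal approximation): about 69%

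For comparison, splitting alpha at 0.025 each would lower %BAD power at 0.37 to 71%, and 72 pairs would be needed to restore 80%.

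**4. The conversion to 1.5 points (minor).**
- If 4 is the SD of the within-subject difference, 1.5 points is 1.5/4 = 0.375 SD and power is 82%. The statement stands.
- If 4 is the SD of one measurement, equal in both periods, then SD of the difference = 4 × √(2(1 − rho)), and the difference detectable with 80% power = 0.3677 × that SD.

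| rho (assumed) | SD of difference | Detectable with 80% power | Power for 1.5 points |
|---|---|---|---|
| 0.3 | 4.73 | 1.74 | 68% |
| 0.4 | 4.38 | 1.61 | 74% |
| 0.5 | 4.00 | 1.47 | 82% |
| 0.6 | 3.58 | 1.32 | 89% |
| 0.7 | 3.10 | 1.14 | 96% |

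Break-even: 80% power at 1.5 points allows an SD of the difference of at most 1.5/0.3677 = 4.08. This corresponds to rho = 1 − (4.08/4)²/2 = 0.48.

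**The case against.** **On the success rule.** No section says that a win on either outcome would count, so 9.75% is a conditional figure. A reader might infer that the plan inflates its error rate to that level. The documents do not support this, because they do not say what counts as success; the defect is the silence. A reader might equally infer from section 15.4 that %BAD already ranks first. That section gives %BAD priority only for sizing and sets no testing order. Other rules, such as requiring both outcomes, splitting alpha or naming a single primary, would also close the gap, and ordered testing does demote PAT. All of this stands. It leaves the need for a rule intact and makes the choice among rules a matter of cost.

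**On the SD.** Section 15.2 ties 0.37 to the change in %BAD between periods and then gives the SD, so 4 may be the SD of that same change, loosely labelled. The section also admits that power under the final mixed model is hard to estimate because the residual variability is unknown. The first argument has real force: taken alone, this is mostly a labelling query. The caveat about the mixed model concerns covariate adjustment and does not identify the SD. A reader might go further and conclude that the trial is underpowered for 1.5 points. The documents do not support that: power for 1.5 points is below 80% only if 4 is a single-measurement SD and rho is below 0.48, and they establish neither. Aim 2 needs no separate criticism, since it makes no raw-scale conversion and its units follow from the same paired test.

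**Conclusion.** The main point holds as a cheap improvement. Two equally ranked primary outcomes are each tested at unadjusted 0.05, and no success rule is given in the text available for review. Should either outcome suffice, the family-wise error is 9.75% (independent) or about 9.1% (test correlation 0.5, assumed).

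The SD point is minor. The sample size, the power and the product 0.37 × 4 are all correct. What is missing is the identity of the SD, and the direction of any error in the 1.5-point figure cannot be settled from the documents. Under the single-measurement reading, with equal SDs in both periods, the detectable difference runs from 1.74 to 1.14 points as rho goes from 0.3 to 0.7. These figures are for the paired t-test of section 15.2; the adjusted mixed model of section 15.1 may differ.

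**What to change.** **Section 15.1.** Add a rule: test %BAD first at two-sided 0.05, and test PAT at two-sided 0.05 only if %BAD is significant. The reason for this order is that the trial is sized on %BAD. Align the synopsis and sections 5.2 and 12.1. No subjects are added and %BAD power is unchanged. The cost is that PAT loses its stand-alone primary status, and its chance of being claimed falls from 80.5% to about 65–69% if its effect is also 0.37.

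**Section 15.2.** State the SD of the within-subject sildenafil-placebo difference that was used. If 4 is that SD, relabel it and keep 1.5 percentage points. If 4 is any other SD, such as that of a single measurement or of change from period baseline, state the assumed correlation and restate the detectable difference. For a single-measurement SD of 4, equal in both periods, this is 1.74, 1.47 or 1.14 points at rho 0.3, 0.5 or 0.7. This is a wording change only. N and the analysis stay as they are, but the 1.5-point claim may become conditional.

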15.3 POTENTIAL PITFALLS AND SOLUTIONS

15.3.1 How will we account for the potential variability in results of brachial artery FMD measurements?

A number of factors may potentially influence the results of brachial artery FMD. To account for this, subject-specific factors will be minimized by requesting subjects to limit antioxidant vitamin and/or antioxidant-rich diet within 72 hours; document use of CV medications (e.g., β -blockers, calcium channel blockers, NSAIDs, and aspirin); limit tobacco and caffeine use within 12 hours; document the phase of menstrual cycle for premenopausal women (since optimum time for FMD studies is days 1-7 of menses); abstain from exercise within 12 hours; and be fasting and rested before the FMD study. Finally, since we recognize there is diurnal variation in the FMD response, we will attempt to schedule each subject's visits at consistent times of the day.

15.3.2 What if study subject recruitment and retention rates are slower and/or less than anticipated?

We will increase advertising efforts and may open the study at other community rheumatology clinics, with over 6,000 active RA patients. We may include those on statins, ACE-i or ARB (on stable dose x 4+ months), and retain subjects with RA medication changes. We will address these factors statistically, if needed.

15.3.3 How will the effect of comorbidities and RA disease-related factors that affect endothelial function be mitigated so as not to confound the results of sildenafil's effect on endothelial function?

A potential confounder is the effect of traditional CVD risk factors (e.g., DM), CV medications, RA medications, disease activity and duration on potential change in endothelial function over time. As described in Section 4.4, we plan to adjust for these through multivariable linear mixed models. Furthermore, subjects who require a new start or change in RA medication or glucocorticoid maintenance dose increase to 10 mg/day or greater for 4+ weeks during the trial will be withdrawn from the study. Since this is a randomized placebo-controlled study, we anticipate the frequency of these potential confounders will be similar between groups.

15.3.4 Will potential effects of sildenafil risk un-blinding due to altered erectile function or headaches?

Potential effect on erectile function is unlikely to be recognized by male subjects unless they already suffer from ED, in which they will likely already be taking PDE inhibitors and will thus be excluded. Further, most RA patients are women. Per Micromedex, headaches were only seen in 21% of ED subjects taking the 50 mg daily dose (vs. 7% in placebo). Although these potential side effects may unblind subjects, the outcome measures in this study (vascular function and serum biomarkers) are unlikely to be affected by subject un-blinding. Different study personnel will collect AE data vs. other outcome data, to minimize risk of un-blinding.

15.4 Interim Analyses

Potential non-compliance (assessed via pill counts) will be analyzed using intention-to-treat strategy, and for missing data, we will conduct a sensitivity analysis to conservatively assess observing how the worst outcome (of %BAD) would affect results. The test of a treatment \times period interaction is not possible in the given cross-over design since it is confounded by the group effect.

We do not anticipate many subjects with RA or CV medication changes, since inclusion criteria state no expected therapy changes over next 6 months. Moreover, such changes are unlikely to occur systematically more often in the initial sildenafil vs. placebo groups. However, in the event there are many with such changes, we will also conduct a secondary sensitivity analysis including them to assure this does not affect results. The %BAD was chosen as the primary outcome on which to calculate sample sizes based on clinical considerations. Specifically, %BAD has been validated longer and in more populations than PAT.

16. QUALITY ASSURANCE

16.1 Data recording

All data will be entered into the secure Rheumatic Disease Management System (RDMS), which is a Division-wide system for rheumatologic research. A source document checklist will be used at the site to identify the source data for all data points collected.

16.2 Archiving

Documents shall be archived safely and securely in such a way that ensures that they are readily available if required, and in compliance with the University of Pittsburgh guidelines. According to the University of Pittsburgh IRB, all study-related documents will be stored for 7 years. The investigator site file is not to be destroyed without approval by NIAMS or the Safety Monitor.

16.3 Publication Policy

Following completion of the SEDRA study, the investigators will publish the results of this research in scientific journals. The International Committee of Medical Journal Editors (ICMJE) member journals has adopted a trials-registration policy as a condition for publication. This policy requires that all clinical trials be registered in a public trials registry such as ClinicalTrials.gov, which is sponsored by the National Library of Medicine. The SEDRA study is registered with ClinicalTrials.gov, with number NCT02908490.

As this is a single-center study, there will be no publications committee. Authorship determination will be made in consultation with the co-investigators of the study.

Publication of the results of this trial will be governed by NIAMS publication policies. Any presentation, abstract, or manuscript will be made available for review by the NIAMS supporters prior to its submission. [name] will maintain control of all SEDRA-generated specimens and will decide on the scientific merit of any future sub-studies. They will adhere to the letter and the spirit of the prevailing NIH and NIAMS guidelines on the sharing of research resources produced from federally-funded research. Specifically, any publications will be submitted, as required, to the NIH National Library of Medicine PubMed central for archiving upon acceptance for publication. These policy details (<http://grants.nih.gov/grants/guide/notice-files/NOT-OD-05-022.html>) will be adhered to.

16.4 Confidentiality / HIPAA

This is a single-center study, with a relatively small number of subjects. All personnel involved in this study have undergone training and certification on the protection of human subjects, confidentiality, HIPAA compliance and research integrity. This training is conducted regularly by the University of Pittsburgh via an internet-based system of education in research.

The only individuals with access to identifiable information and treatment assignment will be the data manager and study statistician. Access to study data will be password protected. All linkage materials are stored separately and maintained in a secure area.

All blood samples will be collected in a de-identified manner using labels generated through the RDMS system. Linkage codes will be maintained by the data manager in the event of emergencies or future need, and these will be kept in a locked filing cabinet located in the Division of Rheumatology research office.

ETHICAL AND LEGAL CONSIDERATIONS

16.5 Ethical and legal conduct of the study

The procedures set out in this protocol, pertaining to the conduct, evaluation, and documentation of this study, are designed to abide by GCP guidelines and under the guiding principles detailed in the Declaration of Helsinki. IRB approval has been obtained. The investigator may implement a deviation from, or a change of, the protocol to eliminate an immediate hazard(s) to the trial subjects without prior IRB approval. As soon as possible, the implemented deviation or change, the reasons for it and if appropriate the proposed protocol amendment will then be submitted to the University of Pittsburgh IRB. Any deviations from the protocol will be explained and documented by the investigator. Protocol deviations will also be reported biannually to the Safety Monitor.

16.6 Subject information and consent

The investigator will discuss that written approval of the IRB has been obtained. Consent forms, describing in detail the therapies, procedures, and risks, will be given to the participant, and written documentation of informed consent is required prior to starting the study agent(s). Consent forms will be IRB-approved, and the participant will be asked to read and review the document. Upon reviewing the document, the study coordinator will explain the research study to the participant and answer any questions that may arise. The participants will sign the informed consent document prior to any procedures being done specifically for the study. The participants will have sufficient opportunity to discuss the study and process the information in the consent process prior to agreeing to participate. Only if the subject voluntarily agrees to sign the informed consent form and has done so, may s/he enter

the study. Additionally, the PI will personally sign and date the form. The subject will receive a copy of the signed and dated form. The signed informed consent statement is to remain in the investigator site file. In the event that informed consent is obtained on the date that baseline study procedures are performed, the study record or subject's clinical record must clearly show that informed consent was obtained prior to these procedures.
